## C. APPROACH

### C.1. Product evaluation.

We will conduct an evaluation of the CoQuit app with a nationwide sample of 500 adults who are daily smokers. Feasibility, usability, participant satisfaction, and intervention outcomes of cigarette use will be evaluated in an efficacy trial. Data on: 1) frequency and duration of app use, 2) number of modules completed, 3) changes in measures of cognitive dissonance, 4) changes in readiness to quit, and 4) changes in smoking attitudes and behaviors (including quit attempts, number of days without smoking, and co-use of other forms of tobacco, including e-cigarettes) will be examined. Participants will be compensated using gift cards to Amazon with \$25 each for the baseline, 1-month and for the 3-month assessment. In addition, each participant who completes all three assessments will receive a bonus payment of \$50. We estimate that 75% of participants will receive the bonus payments. Participants in the focus groups and usability testing will receive a \$50 gift card for their time and effort.

**C.2. Study Design.** Our evaluation of the CoQuit app will be conducted with 500 adults who are daily smokers who will be recruited through social media. Participants will be randomly and equally assigned to one of two conditions: 1) CoQuit with CDI (cognitive dissonance induction), or 2) CoQuit content without CDI. All participants will be instructed to attempt to reduce cigarette use and to identify a target quit date at program initiation. Self-reported cigarette use and readiness to quit will be measured at 1-month and 3-month assessments. In addition, we will measure changes in cognitive dissonance for participants in the CoQuit CDI group. Cognitive dissonance measures will be completed after each cognitive dissonance activity, as well as at each of the baseline, 1-month and 3-month assessments.

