### C.4. Overview of the Proposed Intervention Conditions

We propose to randomize participants into one of two conditions, outlined below.

**CoQuit with CDI.** Participants who are randomized to the CoQuit with CDI will be sent access information and instructions and access code for downloading the CoQuit CDI app from the app store immediately following their baseline assessment. Once the app is loaded onto their phone, participants will be assigned to a group of 8 daily smokers who are intended to move through the app at a similar pace. The proposed modules will each include an instruction video that outlines a cognitive dissonance inducing activity that participants will be instructed to record and upload to the app for all group members to see. Modules will be “unlocked” in ascending order as participants move through the program (i.e., module 2 will be “unlocked” after a participant completes module 1, etc.). In addition, participants will receive 2 smoking cessations tips per day to assist with reducing cigarette use and increasing motivation to quit.

**CoQuit without CDI (comparison condition)** Participants who are randomized to the CoQuit without CDI will be sent access information, instructions and an access code for downloading the CoQuit app from the app store immediately following their baseline assessment. Once the app is loaded onto their phone, participants will be free to login and use the app as often as they want. Daily tips and guidance in reducing smoking and increasing motivation to quit will be provided at least once daily. The content and look and feel of this comparison condition will match the CoQuit with CDI but lack any cognitive dissonance activities.

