A full description of measures is included in the Human Subjects. Briefly, the following will be used to examine pre- and post- changes in smoking behavior, cognitive dissonance, and motivation to quit: 1) Nicotine Dependence, 2) Past and Current Tobacco Use (including e-cigarettes), 3) Motivation to Quit, 4) Quit Attempts, and 5) Cognitive Dissonance. Nicotine dependence will be measured at baseline and at each follow-up assessment using the Fagerström Test for Nicotine Dependence and items that assess withdrawal experiences. Past and current tobacco use will be assessed at each time point, including type (including e-cigarettes), frequency, and duration of use. Motivation to quit will be assessed at baseline by asking participants if they want to quit within the next 30 days and at follow-up assessments in terms of stages of change. We will also use an adaptation of the Contemplation Ladder that we have used extensively in our prior research and have found in predicting tobacco cessation. Quit attempts will be measured by the number of intentional quit attempts that last at least 24 hours, duration of quitting, and use of pharmacological adjuncts at each time point. Cognitive dissonance will be measured using the Dissonance Thermometer. Prior research has shown that the 3-item discomfort factor of the Dissonance Thermometer represents the affective expression of cognitive dissonance. Cognitive dissonance will be assessed after each cognitive dissonance activity, as well as at each of the baseline, 1-month and 3-month assessments.

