Title: A Mobile App Based Cognitive Dissonance Intervention for Smoking Cessation

NCT Number: NCT05797155

Date: 3/15/2025

The study included a group-delivered intervention and an ungrouped control condition, creating a partially nested design. The models allowed for between-cluster variability in the outcomes solely within the intervention group to reflect the partial clustering of the data (Baldwin et. al., 2011). Logistic regression models were estimated with a binomial distribution and logit link using the SAS software (Version 9.4) with SAS PROC GLIMMIX and used to test for condition differences (1 =  $S2Q$ , 0 = control), separately at 1- and 3-month follow-up, for the dichotomous outcomes. Odds ratios (ORs) were reported as a measure of effect size, following conventional benchmarks: 1.5 (small), 2.5 (medium), and 4.3 (large; Chen et al., 2010). To address missing data, models were estimated with 20 imputed datasets using SAS PROC MI, and results were combined using SAS PROC MIANALYZE. Mixed-effects growth models were used to evaluate condition differences in the continuous Fagerstrom outcome. The baseline was defined as the random intercept, and the model included fixed effects variables for time, measured in months since the baseline assessment, the randomized condition variable (1 =  $S2Q$ , 0 = control), and a time-by-condition interaction term. The interaction term estimates the change in the outcome from baseline to 3-month follow-up for the intervention condition relative to the control condition. Models were estimated with maximum likelihood using all available data. Cohen's  $d$  was provided as a measure of effect size using conventions: 0.2 (small), 0.5 (medium), and 0.8 (large).

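### The Fagerström growth model estimates a separate baseline mean in each randomised arm, which makes the time-by-condition effect less precise than it need be

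*SAP*

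**What the plan says.** The SAP has one unnumbered section. For the continuous Fagerström outcome it states: "The baseline was defined as the random intercept, and the model included fixed effects variables for time, measured in months since the baseline assessment". It then adds "the randomized condition variable" and its product with time. The treatment effect is the interaction: "The interaction term estimates the change in the outcome from baseline to 3-month follow-up for the intervention condition relative to the control condition". On estimation: "Models were estimated with maximum likelihood using all available data". It mentions no constraint of equal baseline means and no other baseline adjustment.

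The protocol supplies the design facts:
- Section C.2: "Participants will be randomly and equally assigned to one of two conditions", and "Self-reported cigarette use and readiness to quit will be measured at 1-month and 3-month assessments".
- Section C.4: access to the app is sent so that it can be downloaded "from the app store immediately following their baseline assessment". In the CDI arm, groups of 8 form only once the app is on the phone.
- Section C.5.2: "Nicotine dependence will be measured at baseline and at each follow-up assessment using the Fagerström Test for Nicotine Dependence".

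The score is therefore available at months 0, 1 and 3 in both arms, and the first value precedes any exposure.

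**The concern.** Time is counted from the baseline assessment, so the modelled mean at time 0 is b0 in control and b0 + b(condition) in the intervention arm. It is the condition main effect, not the random intercept, that gives each arm its own baseline mean. Under random allocation with exposure after baseline, the true value of that coefficient is zero. Estimating it has two consequences:

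- **Precision.** The interaction becomes a contrast of changes from baseline. It forgoes the gain from using baseline as a shared starting point, so its standard error is larger than the same data allow.
- **Imbalance.** If one arm happens to start higher, regression to the mean pulls that arm down over follow-up, and the change contrast counts the pull as part of the effect.

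At stake is the precision of the treatment effect on the only continuous outcome for which the SAP specifies a model.

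**Working it through.** The documents give no power, precision or sample-size calculation for this outcome, so there is no stated figure to reproduce.

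**Inputs from the documents.** Times t = 0, 1, 3 months. 500 participants allocated equally, so n = 250 per arm (protocol C.2). Protocol C.1 expects 75% to receive the bonus for completing all three assessments; this is used as the completion rate.

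**Assumed inputs.** Score SD 1; within-person correlation ρ; two-sided 5% test; 80% reference power. The remaining 25% are split into 10% with baseline and month 1, and 15% with baseline only. The base case has no group effect.

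**Formulas.** For each missing-data pattern, with V the random-intercept covariance matrix of its visits, define a = 1′V⁻¹1, b = 1′V⁻¹t and c = t′V⁻¹t. For k visits:
- a = k / (1 + (k−1)ρ)
- b = Σt / (1 + (k−1)ρ)
- c = [Σt² − ρ(Σt)² / (1 + (k−1)ρ)] / (1−ρ)

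Let A, B and C be their averages weighted by pattern frequency. With equal arms:
- SAP model: Var(interaction) = (2/n) × A / (AC − B²)
- Common baseline mean: Var(interaction) = (2/n) / C
- Ratio, constrained to SAP: 1 − B² / (AC)

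**Worked case, ρ = 0.7.**
- Three visits: a = 3/2.4 = 1.250; b = 4/2.4 = 1.667; c = (10 − 11.2/2.4)/0.3 = 17.778.
- Two visits: a = 2/1.7 = 1.176; b = 1/1.7 = 0.588; c = (1 − 0.7/1.7)/0.3 = 1.961.
- Baseline only: a = 1; b = c = 0.
- Weighted 0.75/0.10/0.15: A = 1.205, B = 1.309, C = 13.529.
- Ratio = 1 − 1.309²/(1.205 × 13.529) = 0.895.
- SE of the 3-month effect: SAP 3 × √(0.008 × 1.205/14.592) = 0.0771; constrained 3 × √(0.008/13.529) = 0.0730.
- Power: Φ(2.802/√0.895 − 1.960) = 84.2%.

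**Results.**

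| ρ | Ratio, complete data | Ratio, 75% completing | 3-month SE, SAP → constrained (75% completing) | Power from 80% (75% completing) |
|---|---|---|---|---|
| 0.5 | 0.778 | 0.809 | 0.0987 → 0.0888 | 87.6% |
| 0.6 | 0.828 | 0.854 | 0.0887 → 0.0819 | 85.8% |
| 0.7 | 0.875 | 0.895 | 0.0771 → 0.0730 | 84.2% |
| 0.8 | 0.919 | 0.933 | 0.0632 → 0.0611 | 82.7% |
| 0.9 | 0.961 | 0.968 | 0.0449 → 0.0441 | 81.3% |

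**Sensitivity.**
- Random slope added (variance 0.02 to 0.03, uncorrelated with the intercept), 75% completing: ratios 0.880–0.890 at ρ = 0.6, 0.919–0.927 at 0.7 and 0.953–0.959 at 0.8, a cut of about 4% to 12%. With complete data the cut is 5% to 14%.
- Wider slope settings (variance 0.01 to 0.05, intercept–slope correlation 0 or −0.3, ρ = 0.5 to 0.8): ratios 0.76 to 0.97.
- Intervention-arm groups of 8, intraclass correlation 0.02 to 0.05, complete data, ρ = 0.5 to 0.8: ratios 0.80 to 0.95.

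The constrained model had the smaller variance in every setting.

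**Carry-over of imbalance (complete data).** The SAP model's slope weight on the baseline row is (0 − 4/3)/4.667 = −0.286. A chance baseline difference of d SD shifts the 3-month estimate by 3 × (−0.286) × (1 − ρ) × d, which is −0.34d, −0.26d and −0.17d at ρ = 0.6, 0.7 and 0.8. The SE of the baseline difference is √(2/250) = 0.089 SD, so an imbalance of that size moves the estimate by about 0.03, 0.02 and 0.015 SD. In the constrained model the shift is zero. The SAP's benchmark for a small effect is 0.2.

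**The case against.** The strongest reply is that nothing here is an error. A growth model with a condition main effect is a standard specification, its interaction is unbiased over randomisation, and the documents promise no precision or baseline adjustment that it breaks. That stands: the point is about efficiency.

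The gain is also modest. Complete-data figures (17%, 12% and 8% at ρ = 0.6, 0.7 and 0.8) overstate it, given the protocol's 75% estimate, and it nearly vanishes if scores are very stable over three months. That stands too, and the dropout-adjusted figures are the ones to use.

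The outcome is not the trial's focus. Protocol C.5.1 puts the 3-month emphasis on point-prevalence and sustained abstinence, which the SAP analyses by separate logistic models.

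Finally, the SAP is dated March 2025 and written in the past tense. If the analysis has been run, replacing the main model with a more powerful one would be post hoc. This limits how the fix is presented, not whether it is sound.

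A reader might infer that the planned estimate is biased, or that the cessation results are compromised. The documents support neither. Nor does randomisation make the observed baseline means equal. It makes them equal in expectation, and that is all the constrained model uses.

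**Conclusion.** The point holds as a loss of efficiency of small to moderate size, confined to the Fagerström outcome. With 75% completing, the avoidable part of the interaction variance is about 15%, 10% and 7% at correlations of 0.6, 0.7 and 0.8, equivalent to about 17%, 12% and 7% more participants (1/0.854, 1/0.895, 1/0.933). The standard error falls by about 8%, 5% and 3%, and power gains about 3 to 6 points from an 80% reference.

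The direction follows from the design; the size rests on assumptions. The documents state no SD, within-person correlation, intraclass correlation, alpha or power, and the split of incomplete follow-up is assumed. The common baseline mean also requires that all randomised participants with a baseline are analysed. Using all available data is consistent with that, but the SAP defines no analysis set. The change is worth making because it is nearly free, not because the planned analysis is invalid.

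**What to change.** 1. Fit the growth model with fixed effects for time and time-by-condition only, so that both arms share one baseline mean.
2. Keep the baseline score as an outcome row for every randomised participant, including those with no follow-up, and state this as the analysis set.
3. Let the intervention-group random effect act only on the 1-month and 3-month rows, because the groups do not exist at baseline.
4. Report the free-baseline model alongside as a check.
5. State whether results had been seen when the change was made. If they had, label the constrained model as added and report both fits.

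The cost is one fixed effect removed, a restriction on the group random effect and one additional fit to report. No new data are needed.

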Of particular relevance, cognitive dissonance approaches have also shown success in treating substance use, reducing the initiation of smoking, and improving short-term outcomes for smoking cessation. In one study, [name] et al. demonstrated greater quit rates at one-month follow up for smokers who engaged in video-taped discussions of the consequences of smoking delivered via computer. Although prior study results are promising, no long-term significant outcomes have been found, which suggests that increased exposure to dissonance induction activities (dosage) and reach of cognitive dissonance induction approaches might yield improved smoking abstinence outcomes. Guided by prior research, the proposed cognitive dissonance intervention (CDI) specifically provides increased opportunity for exposure to cognitive dissonance by including dissonance induction activities in each of the proposed modules. In particular, we propose to offer the participant multiple opportunities for counter-attitudinal activities and public statements. Additionally, the mobile app format allows for increased access and reach of the intervention. The CDI app will be based on prior cognitive dissonance intervention activities that have demonstrated effectiveness and will specifically

build on consultant [name]' prior work with cognitive dissonance induction via video-recorded tasks for smoking cessation.

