## C.5. Data Collection Procedures

### C.5.1. Overview and timeline for the evaluation study.

The baseline assessment will primarily measure participant risk factors, as well as past and current cigarette and other tobacco use, readiness to quit, quit attempts and cessation in the past year, and will consist of questionnaires administered using Qualtrics; none of the assessments will be done via the mobile app.

The 1-month assessment will focus on usability, cognitive dissonance, motivation to quit, and short-term outcomes such as making a quit attempt, use of the app (dosage), number of cigarettes smoked, and days abstinent from smoking. For the 3-month assessment, the focus will be on cessation outcomes, including both point prevalence (i.e., no smoking in the past 7 days; no smoking in the past 30 days) and sustained abstinence, which is defined as sustained abstinence between the 1-month and 3-month assessment. We will also assess quit attempts at each assessment. Non-responders to the request to complete a follow up assessment will be sent email and text messages to encourage completion of the assessment. We will continue to prompt completion for 14 days following the initial request for the one month assessment and there will be a 30 day window for completion of the 3-month assessment.

**C.5.2. Measures.** Program navigation and usability will be assessed during usability testing and for the evaluation participants over the one month of use, and will include reports of: 1) ease of use, 2) perceived benefits of using the app, and 3) suggestions for product development modifications. Participants will also provide ratings on product satisfaction and usability on a 7-point Likert Scale. In addition to qualitative data, login tracking information from the app will be used to assess each participant's: 1) frequency and duration of app use, 2) number of modules completed, and 3) type and frequency of cigarette use. These data will be used to evaluate treatment engagement and adherence, as well as pre- and post- changes in tobacco use.

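### The Fagerström growth model's single time-by-condition term equals the 3-month difference the SAP says it estimates only if the arm difference grows in a straight line over 0, 1 and 3 months

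*SAP*

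**What the plan says.** The SAP (one unnumbered section) analyses the Fagerström score with a mixed-effects growth model. "The baseline was defined as the random intercept", and the fixed effects are "fixed effects variables for time, measured in months since the baseline assessment", the randomised condition, "and a time-by-condition interaction term". It names no quadratic, piecewise or categorical time term and gives no visit-specific contrast for this outcome. It interprets the model as follows: "The interaction term estimates the change in the outcome from baseline to 3-month follow-up for the intervention condition relative to the control condition". On missing data: "Models were estimated with maximum likelihood using all available data".

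Protocol section C.5.2 has the Fagerström test given at baseline and at each follow-up, so months 0, 1 and 3 all enter the model. The SAP treats the dichotomous outcomes differently, testing condition separately at 1 and at 3 months.

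**The concern.** The SAP does not use the word linear, but numeric time with a single interaction amounts to it: one slope difference per month and nothing else. The 3-month arm difference is then read off a line fitted through three unequally spaced visits, and the 1-month difference affects it. If the true difference rises early and then levels off or declines, the fitted line gives neither the 1-month nor the 3-month effect.

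Such a shape is plausible here. Protocol section C.5.2 refers to usability reports "for the evaluation participants over the one month of use", and section A describes better quit rates at one month in earlier dissonance work, then adds: "Although prior study results are promising, no long-term significant outcomes have been found". This is the SAP's only analysis of a continuous outcome, and its stated meaning depends on an assumption the SAP does not mention.

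**Working it through.** The documents give no effect size, SD, correlation or power for the Fagerström outcome, so there is no figure of the plan's own to reproduce.

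**Inputs from the documents**
- Visits at 0, 1 and 3 months (protocol C.2 and C.5.2).
- 500 participants allocated equally, so 250 per arm (C.2).
- An expected 75% earning the bonus for completing all three assessments (C.1).
- A 14-day prompting period at month 1 and a 30-day window at month 3 (C.5.1).

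**Weights with complete data.** Let D0, D1 and D3 be the arm differences, with benefit positive.
- Mean time = (0 + 1 + 3)/3 = 4/3.
- Sum of squares = (4/3)² + (1/3)² + (5/3)² = 42/9 = 14/3.
- Slope weight = (t − 4/3)/(14/3), giving −2/7, −1/14 and +5/14.
- Multiplied by 3 months: −0.857, −0.214 and +1.071.

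Generalised least squares with a random intercept gives the same weights at any within-person correlation, and a cluster intercept in the intervention arm does not change them. Randomisation makes D0 zero in expectation, so the 3-month estimate is 1.071 × D3 − 0.214 × D1. If the effect is truly linear (D1 = D3/3), this is 1.071 × D3 − 0.071 × D3 = D3, as it should be.

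**Other shapes, with a true 1-month effect of 1**

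| True 3-month effect | Straight-line estimate | Error |
|---|---|---|
| 1 (plateau) | 0.857 | −14% |
| 0.5 (half faded) | 0.536 − 0.214 = 0.321 | −36% |
| 0.2 | 0.214 − 0.214 = 0 | break-even |
| 0 (all lost) | −0.214 | wrong sign |

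The break-even is 0.214/1.071 = 20% of the 1-month benefit remaining.

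**Incomplete data.** These are random-intercept GLS weights scaled to 3 months, for assumed correlations of 0.5 to 0.7.

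| Pattern (assumed) | Month-1 weight | Plateau estimate |
|---|---|---|
| 25% miss month 3 only | −0.12 to −0.11 | 0.92 to 0.93 |
| 12.5% miss month 3 only, 12.5% have baseline only | −0.15 to −0.14 | 0.90 to 0.91 |
| 25% have baseline only | −0.19 to −0.17 | 0.88 to 0.89 |
| 40% miss month 3 only | −0.02 to −0.01 | 0.985 to 0.99 |
| 50% miss month 3 only | +0.07 to +0.08 | 1.04 to 1.05 |

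In the first two patterns the plateau is understated by about 7 to 10%.

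**Elapsed instead of nominal time.** If actual dates are used, with complete data, the month-1 weight is −0.23 for visits at 0/1/4 months, −0.13 at 0/1.46/4 and −0.02 at 0/1.46/3. Here 1.46 is one month plus 14 days, and 4 is three months plus the 30-day window.

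**What the straight line gains.** With equal correlations and complete data, Var(3 × slope)/Var(3-month change) = 1.929/2. The SE ratio is √0.964 = 0.982, so the line's SE is 1.8% smaller.

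**Illustrative power.** Assumptions: 250 per arm, complete data, no clustering, two-sided 0.05, correlation 0.6.
- 3-month effect 0.25 SD, plateau: 78% (straight line) against 88% (categorical).
- 3-month effect 0.25 SD, half faded (1-month effect 0.50 SD): 53% against 88%.
- 3-month effect 0.20 SD, truly linear: 72% against 71%.

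**The case against.** A straight line through three visits is a common growth model. No passage names Fagerström as the primary outcome, protocol C.5.1 puts the 3-month focus on cessation, and the dichotomous outcomes are not forced onto a line. All of that stands, and it limits the point to one continuous outcome.

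Three stronger readings are tempting, and the documents do not support them.

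- **That an early benefit always counts against the intervention, or that the model will show harm.** The month-1 weight is one fifth of the month-3 weight with complete data. It roughly halves if 25% miss month 3 only, nearly vanishes at 40%, and is positive at 50%. A wrong sign needs almost all of the 1-month benefit to have gone.
- **That the protocol's own evidence shows an early peak.** The evidence in section A concerns quit rates, not Fagerström scores. A lack of significant long-term results is not a demonstrated fade, and long-term is not defined as 3 months. The protocol also says the app increases exposure to address that limit. The words on one month of use come from the paragraph on usability measures.
- **That the trial loses a known amount of power.** The power figures rest on assumed effects and correlation, and they leave out dropout and the intervention-arm clustering.

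None of this rescues the SAP's interpretive sentence, which is exact only under linearity. That the weights move with dropout and with the time coding is a further reason not to rest a 3-month claim on them.

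**Conclusion.** The concern holds in a limited form and should be fixed. The interaction coefficient is per month. Multiplied by 3, it is the 3-month difference only if the arm difference grows linearly. With complete data at nominal times the understatement is about 14% for a plateau and about 36% for a half-faded benefit, and this is algebra that needs no assumed SD or correlation. The sizes under missing data depend on the assumed dropout patterns and correlations, and on whether time is nominal or elapsed, which the SAP leaves open. A non-linear effect is plausible, but a fading Fagerström effect is not established. The cessation analyses are untouched.

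**What to change.** Fit assessment (baseline, 1 month, 3 months) as a categorical factor with assessment-by-condition terms, keeping the partial-nesting structure. Report the arm difference in change from baseline at 3 months as the Fagerström result, with the 1-month contrast alongside. With complete data these contrasts are D3 − D0 and D1 − D0, so month 1 carries no weight in the 3-month result. Keep the straight-line model as a labelled sensitivity analysis. There, state that its coefficient is per month, and say whether time is nominal or elapsed.

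The SAP is written in the past tense, so the analysis may already have been run. In that case, label the categorical model as a post hoc re-analysis and show both results.

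The change uses data already planned for collection and brings this outcome into line with the visit-specific tests of the dichotomous ones. The cost is a revised SAP paragraph and one more model run. If the effect is truly linear, the SE is also about 2% larger with complete data, or about one point of power in the 0.20 SD illustration.

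### The SAP describes the Fagerström time-by-condition coefficient as a baseline-to-3-month difference, but as specified it is a difference per month, and multiplying by 3 recovers the month-3 difference only if the effect is linear

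*SAP*

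**What the plan says.** The SAP is a single unnumbered section. For the continuous Fagerström outcome it specifies a mixed-effects growth model with "fixed effects variables for time, measured in months since the baseline assessment", a condition indicator (1 = S2Q, 0 = control) and "a time-by-condition interaction term". It interprets the last of these as follows: "The interaction term estimates the change in the outcome from baseline to 3-month follow-up for the intervention condition relative to the control condition". Cohen's d "was provided as a measure of effect size using conventions" of 0.2, 0.5 and 0.8, with no formula. The dichotomous outcomes are handled differently: condition is tested "separately at 1- and 3-month follow-up, for the dichotomous outcomes". On clustering, the SAP states: "The models allowed for between-cluster variability in the outcomes solely within the intervention group".

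Protocol section C.5.2 says: "Nicotine dependence will be measured at baseline and at each follow-up assessment". Section C.5.1 places the follow-ups at 1 and 3 months, so the model has three time points: 0, 1 and 3. Section C.5.2 also says usability is assessed "for the evaluation participants over the one month of use".

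**The concern.** There are three linked problems.

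- **Scale.** A coefficient on months × condition is a difference in change per month. The SAP describes it as the difference over the whole three months. A reader who takes the reported coefficient and interval at the SAP's word would understate a linear 3-month effect threefold.
- **Shape.** The month-1 value enters the slope, so rescaling to three months gives the month-3 difference only if the effect grows in a straight line. The SAP does not state that assumption. With one month of app use described in the protocol, straight-line growth to month 3 cannot be taken for granted. The SAP does not impose it on the dichotomous outcomes.
- **Effect size.** The SAP gives benchmarks for d but not the estimate or standard deviation behind it. If d were taken from the raw coefficient, it would also be a third of its 3-month value.

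**Working it through.** The documents give no effect, SD or power figure for this model, so there is nothing to reproduce. The check is algebra on the model as written.

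**Inputs from the documents.** Time in months and a single interaction term (SAP); visits at 0, 1 and 3 months (protocol C.5.1 and C.5.2); 75% expected to complete all three assessments (protocol C.1, bonus payments); 14 days of prompting at month 1 and a 30-day period at month 3 (protocol C.5.1).

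**Scale.** Write E[Y] = b0 + b1·t + b2·A + b3·t·A, with t in months and A the arm. The between-arm difference in change from 0 to t is b3·t. At t = 3 it is 3·b3, so b3 alone is one third of the quantity the SAP names. For a linear 3-month effect with d = 0.30, a d built on b3 would be 0.30/3 = 0.10.

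**Shape, complete data.** The mean of (0, 1, 3) is 4/3, and the sum of squared deviations is 16/9 + 1/9 + 25/9 = 42/9 = 4.667. The slope weights are (t − 4/3)/4.667 = (−4, −1, 5)/14. Let d1 and d3 be the between-arm differences in change from baseline at months 1 and 3. Then

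3 × slope = (15·d3 − 3·d1)/14,

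which equals d3 only when d1 = d3/3.

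| Effect shape | d1 | d3 | 3 × slope |
|---|---|---|---|
| Linear | 1/3 | 1 | 1.000 |
| Half by month 1 | 0.5 | 1 | 0.964 |
| Early and sustained | 1 | 1 | 0.857 |
| Late only | 0 | 1 | 1.071 |
| Half faded | 1 | 0.5 | 0.321 |
| Gone by month 3 | 1 | 0 | −0.214 |

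**Power.** Assume equal SDs and no clustering. Over between-visit correlations of 0.5 to 0.7, the SE of the month-3 change contrast is 1.018 to 1.028 times the SE of 3 × slope. Where the month-3 contrast has 80% power (two-sided 5%, z = 2.802), the slope test has z = 2.802 × (3 × slope/d3) × SE ratio:

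| Effect shape | Multiplier of z | Power of slope test |
|---|---|---|
| Linear | 1.018 to 1.028 | 81% to 82% |
| Half by month 1 | 0.982 to 0.991 | 79% |
| Early and sustained | 0.873 to 0.881 | 69% to 70% |
| Late only | 1.091 to 1.102 | 86% to 87% |
| Half faded | 0.655 to 0.661 | 45% to 46% |

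**Sensitivity to dropout.** Take 75% complete and assume the other 25% miss either month 3 only or both follow-ups, completely at random, with a random-intercept fit and an assumed intraclass correlation of 0.5 to 0.7.

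| Effect shape | True d3 | 3 × slope |
|---|---|---|
| Half by month 1 | 1 | 0.97 to 0.98 |
| Early and sustained | 1 | 0.88 to 0.93 |
| Late only | 1 | 1.04 to 1.06 |
| Half faded | 0.50 | 0.35 to 0.41 |
| Gone by month 3 | 0 | −0.19 to −0.11 |

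**Sensitivity to timing.** As an extreme, assume actual elapsed time is used and every follow-up falls at the end of its period (1.46 and 3.99 months). Slope × time of last visit is then 0.98, 0.89, 1.06, 0.36 (true value 0.50) and −0.17 (true value 0), in the same order of shapes. Neither variation changes the picture.

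**The case against.** The strongest reply is that this is wording. The SAP states the time unit openly, its sentence could be read as naming the period over which relative change is modelled, and the factor of 3 does not touch the p-value. A growth model with one interaction is itself a declaration of linearity and a recognised choice. For effects that build or hold, 3 × slope stays within 0.86 to 1.07 of the true value, and for linear or late effects the slope test is slightly more powerful. The large errors need an effect that peaks at month 1 and fades. The phrase about one month of use concerns when usability is assessed and does not say that access ended then. Nothing shows that d came from the raw coefficient. Categorical visits with a random intercept alone may also misstate the SE: under the unequal correlations tried, the reported SE is about 0.86 to 0.94 of the true one.

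Much of this stands as a limit on weight. The p-value point is right, the consequence for d is conditional, and no document establishes fading. But the sentence describes a change between two time points, not a rate, so the coefficient and its interval are misdescribed as written. A linear specification does not tell the reader that the month-3 figure depends on linearity. The SE problem applies about equally to the SAP's own slope model, so it is no argument for keeping that model.

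**Conclusion.** The concern holds and should be fixed. The coefficient as specified is a per-month difference, one third of the quantity the SAP says it estimates when the effect is linear. This reading rests on time being continuous, which follows from the growth model, the unit of months and the single interaction term. Had time been coded so that one unit is three months, the scale point would fall away but linearity would still be needed. Had visits been categorical, the month-3 interaction would be the stated quantity. Neither is written.

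The error from non-linearity is modest for effects that build or hold (−14% to +7% with complete data) and larger for effects that peak early and fade. The power figures rest on assumed correlations and ignore clustering. The reach is limited: neither document names Fagerström as primary, protocol C.5.1 puts the 3-month emphasis on cessation, and the dichotomous analyses are unaffected.

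**What to change.** Analyse Fagerström with visit as a category (0, 1, 3 months), keeping the group effect in the S2Q arm only, and state the within-person covariance. Report the month-3 between-arm difference in change from baseline with its interval. Compute Cohen's d from that contrast, and state the formula and the SD used.

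At minimum, keep the growth model but report 3 × slope (or code time as months/3), base d on that figure, and state that the effect is assumed linear from baseline to month 3.

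Either version needs only SAP wording and a short code change on existing data. With complete data, equal SDs and correlations of 0.5 to 0.7, the categorical contrast has an SE about 2% to 3% larger than 3 × slope. It also gives up the small power advantage the slope test has if the effect is linear or late. The minimum version has no statistical cost.
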